11.1.3 Serious Adverse Event

If an event is not an AE per definition above, then it cannot be an SAE even if serious conditions are met (e.g. hospitalisation for signs/symptoms of the disease under study, death due to progression of disease).

A SAE is defined as any untoward medical occurrence that, at any dose:

Results in death

Is life-threatening

The term 'life-threatening' in the definition of 'serious' refers to an event in which the participant was at risk of death at the time of the event. It does not refer to an event, which hypothetically might have caused death, if it were more severe.

Requires inpatient hospitalisation or prolongation of existing hospitalisation

In general, hospitalisation signifies that the participant has been detained (usually involving at least an overnight stay) at the hospital or emergency ward for observation and/or treatment that would not have been appropriate in the physician's office or outpatient setting. Complications that occur during hospitalisation are AEs. If a complication prolongs hospitalisation or fulfils any other serious criteria, the event is serious. When in doubt as to whether "hospitalisation" occurred or was necessary, the AE should be considered serious.

Hospitalisation for elective treatment of a pre-existing condition that did not worsen from baseline is not considered an AE.

Results in persistent disability/incapacity

The term disability means a substantial disruption of a person's ability to conduct normal life functions.

This definition is not intended to include experiences of relatively minor medical significance such as uncomplicated headache, nausea, vomiting, diarrhoea, influenza, and accidental trauma (e.g. sprained ankle) which may interfere with or prevent everyday life functions but do not constitute a substantial disruption.

Is a congenital anomaly/birth defect

Other Important Medical Event

Medical or scientific judgment should be exercised in deciding whether SAE reporting is appropriate in other situations such as important medical events that may not be immediately life-threatening or result in death or hospitalisation but may jeopardise the participant or may require medical or surgical intervention to prevent one of the other outcomes listed in the above definition. These events should usually be considered serious.

Examples of such events include invasive or malignant cancers, intensive treatment in an emergency room or at home for allergic bronchospasm, blood dyscrasias or convulsions that do not result in hospitalisation, or development of drug dependency or drug abuse.

A suspected or confirmed coronavirus COVID-19 (SARS-CoV-2) infection must be reported as serious (seriousness criteria should be “other medically significant” if no other seriousness criteria are present (e.g. hospitalisation).

Is a suspected transmission of any infectious agent via an authorised medicinal product

Regardless of the above criteria, any additional AEs that the Sponsor or an Investigator considers serious should be immediately reported to the Sponsor. Any onset or recurrence of neoplasia must also be reported as an SAE.

11.1.4 Deaths

All AEs resulting in death must be reported as an SAE within 24 hours of the Investigator's knowledge of the event. All fatal outcomes should be considered as AEs, even if this fatal outcome is not considered to be related to the medicinal product. The convention for recording death is as follows:

- AE term: lead cause of death (e.g. multiple organ failure, pneumonia, myocardial infarction); *death is not an event term*.
- Outcome: fatal.

The **only exception** is if the cause of death is unknown (i.e. sudden or unexplained death), in which case the AE term may be ‘Death’ or ‘Sudden death’.

11.1.5 Targeted Adverse Events

The targeted AEs for this registry are:

- (1) **During the treatment period:** hypersensitivity; scoliosis; immunogenicity (presence of antibodies if available); slipped capital femoral epiphysis, headache, otitis media, papilloedema, hypoglycaemia (suspected or documented – documented means blood level glucose < 50 mg/dL or 2.78 mmol/L), acromegalic facial changes, gynaecomastia, hearing loss, intracranial hypertension, lipohypertrophy at injection sites, sleep apnoea, tonsillar hypertrophy, cardiomegaly, oedema and myalgia.
- (2) **During the post-treatment period:** All targeted AEs mentioned in the treatment period except lipohypertrophy at injection sites.

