9.2.6 Registry Schedule

The schedule of observations and assessments during the registry are summarised in Table 1.

Table 1 Schedule of Assessments

	Enrolment Visit	Follow-up Visits (in Treatment Period)	Post-treatment Visits
Informed consent ^[a]	X		
Visit date	X	X	X
Eligibility criteria ^[a]	X		
Pregnancy test ^[b]	X		
Demographics	X		
Birth weight and length	X		
Gestational age	X		
Prior heights and sitting heights	X		
Prior weights	X		
Medical history	X		
Personal and family history of neoplasia	X		
Concomitant medications	X	X	X
Parental heights ^[c]	X		
Predicted adult height	X		
Diagnosis of SPIGFD and associated aetiologies	X		
Genetic tests	X		
All AEs, SAEs, AESI, targeted AEs and special situations		X	X ^[d]
Physical examination	X ^[e]	X	X
Height and sitting height	X	X	X
Weight	X	X	X
Pubertal (Tanner) stage	X	X	X
Previous treatments (e.g. GH)	X		
GH concentration ^[f] and stimulation test ^[g]	X		
IGF-1 generation test (if locally applicable) ^[g]	X		
IGF-1 concentration ^[f] ^[g]	X	X	X
IGFBP3 ^[f] ^[g]	X	X	
GHB ^[g]	X		
Bone age, echocardiogram and funduscopic	X	X	X ^[h]
QoL ^[i]	X	X	X
Dose of Increlex® with corresponding dates and compliance	X	X	
Therapy discontinuation		X	
Final Adult Height		X	X

AE = adverse event; AESI = adverse event of special interest; GH = growth hormone; GHBP = growth hormone-binding protein; IGF-1 = insulin-like growth factor-1; IGFBP3 = insulin-like growth factor-binding protein 3; QoL = quality of life; SAE = serious adverse event; SPIGFD = severe primary insulin-like growth factor-1 deficiency.

- a For participants already enrolled in the registry, eligibility must be reconfirmed and a new written informed consent must be obtained for any substantial protocol amendments before implementing them. For any participants enrolled in the registry under previous inclusion/exclusion criteria (i.e. before implementation of Protocol Amendment #6), who would be ineligible according to any of the current inclusion or exclusion criteria, e.g. receiving Increlex® for an indication not covered by the locally approved product information, a letter will be sent to the Investigator to alert him/her about the off-label use of the product (specifically for the risk of neoplasias). The participant could continue to be followed up in the registry for safety data in the post-treatment period

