9.2.9 *Treatment Discontinuation*

If benign or malignant neoplasia develops, Increlex® treatment should be discontinued definitely and appropriate expert medical care sought. If a US patient develops benign neoplasm, Increlex® treatment can continue.

Increlex® treatment may be discontinued in the event of any SAEs, AEs or special situations deemed by the Investigator to warrant treatment discontinuation.

Discontinuation of treatment due to AEs should be distinguished from discontinuation/withdrawal from the registry due to participant/parent decision or end of post-treatment follow up. In all cases due to AEs, the Investigator must ensure that the participant receives appropriate medical follow up and this should be properly documented in the participant's medical records.

All participants discontinuing Increlex® treatment will be followed up in the registry in the post-treatment period (unless consent is withdrawn).

9.3 *Endpoints and Variables*

9.3.1 *Endpoints*

9.3.1.1 *Primary Endpoints*

- Incidence of SAEs (including AESI of neoplasia), targeted AEs, all AEs, deaths and withdrawals due to AEs during Increlex® treatment.

9.3.1.2 *Secondary Endpoints*

- Incidence of SAEs (including AESI of neoplasia), targeted AEs, all AEs, deaths, withdrawals due to AEs, special situations and concomitant medications within the 5-year post-treatment period, overall and in the subset of children and adolescents exposed to Increlex® for at least 3 cumulative years excluding interruptions;
- Incidence of special situations and concomitant medications during Increlex® treatment;
- Changes from baseline for the following effectiveness variables: height SDS, height velocity, body mass index (BMI) SDS, bone age development, pubertal (Tanner) stage;
- Estimation of differences between PAH and FAH;
- Modelisation to identify predictive factors of height SDS change, height velocity, FAH, pubertal (Tanner) stage, bone age development;
- Description of Increlex® therapy exposure (dose and duration) and compliance;
- Description of effectiveness parameters (height SDS, height velocity) according to average dose received and according to dose ranges (e.g. 4 dose ranges (≤ 50 , $]50-80]$, $]80-110]$, $> 110 \mu\text{g/kg BID}$). This analysis will support the description of the lowest effective dose;
- Biological assessments (IGF-1 levels, GH concentrations, serum IGFBP3);
- Genetic test results;

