9.7 Data Analysis

9.7.1 Analyses Population Definitions

At the site level:

Screened: site which has been contacted for participation in the registry and confirmed that they are currently following patients who may be eligible for the registry (this includes both participating and non-participating sites).

Participating: site which has agreed to participate in the registry and has completed a patient screening log (as minimum data requested for participation).

At the patient/participant level:

Screened Population: all patients included in the patient screening log (this includes both enrolled and non-enrolled patients, with the reason for non-enrolment).

Enrolled Population: all participants who are fully informed about the registry and who have given their written informed consent to participate (and/or their parents/legally authorised representatives) before implementation of any registry-related procedure.

Registry Population: all participants who have completed at least one follow-up visit and who have taken the treatment at least once.

Complete Population: all participants who have stopped treatment and who have been followed until FAH reached.

Safety Population: all participants who have taken the treatment at least once and with at least one follow-up visit or presence of any post-study treatment safety data.

Long-term Safety Population: all participants who have been exposed to Increlex® for at least 3 years and who ended therapy at least 2 years prior to the collection of long-term safety data. The primary analysis based on the primary endpoint will be performed on the Safety Population.

9.7.2 *Statistical and Analytical Methods*

9.7.2.1 *Statistical Analyses*

The statistical analyses will be performed by an external SP managed by the Sponsor.

A Statistical Analysis Plan (SAP) describing the planned statistical analysis in detail with tables, figures and listings templates will be developed as a separate document.

Statistical evaluation will be performed using Statistical Analysis System (SAS)[®] (Version 9 or higher).

As this is a non-interventional study, no formal statistical testing will be performed and all the analyses will be primarily descriptive in nature. When appropriate and unless otherwise specified, 2-sided 95% confidence intervals (CIs) will be displayed and if p-values are presented, they will be for exploratory purposes only.

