Descriptive statistics will include number of available data, number of missing data and the following:

- Mean, SD, 95% CIs for means when appropriate, median, quartile, minimum and maximum for continuous variables;
- Frequency count, percentages and 95% CIs when appropriate for categorical nominal variables;
- Both the above for categorical ordinal variables.

Missing data will not be replaced but they will be displayed in all relevant tables.

9.7.2.2 *Participant Inclusion*

Based on the screened population, the proportion of non-included patients will be assessed as well as the reasons for non-inclusion.

9.7.2.3 *Demographic and Other Baseline Characteristics*

Descriptive statistics of demographic and baseline data will be presented for the Registry Population.

Previous/concomitant medications will be summarised by drug categories.

Data on medical history, coded using MedDRA, and previous growth therapy will be summarised.

Information on SPIGFD diagnosis, personal or familial risk factors for neoplasia and genetic test results (deletion/mutation of GH gene, IGF-1 gene, FGF, PTPN11, GHR, D3-GHR, STAT5b, ALS, SHOX, PAPPA2 and any other genetic tests performed, e.g. whole exon sequencing) will be described.

9.7.2.4 *Participant Disposition and Withdrawals*

The numbers and percentages of participants included in the analysis populations will be tabulated overall and by country and site. The reasons for participant exclusions from each of the populations will also be tabulated.

In addition, the number of participants who ended the treatment, withdrew or completed the registry will be presented with the primary reasons for discontinuation.

9.7.2.5 *Primary Analyses*

The primary analyses and summary tables of safety data will be based on the Safety Population (data from the treatment period only).

An overall summary table of AEs during the treatment period (up to 30 days after the last dose) including SAEs, AESI, targeted AEs, all AEs, AEs leading to death and AEs leading to withdrawal will be presented with the number and proportion of participants and the number of events.

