9.9 Limitations of the Research Methods

Following the EU approval of Increlex®, a commitment was made to conduct an EU Subject Registry for Long-term Safety and Efficacy Monitoring of Increlex® for subjects with Growth Failure (to build up a safety and effectiveness database related to the use of Increlex® in paediatric populations) including a commitment to evaluate long-term safety for 100 subjects enrolled in the registry who have been treated with Increlex® for, at least 3 years, with post-treatment safety visits at 2 and 5 years.

As a result of slow recruitment in this long-term safety follow up and considering the Specific Obligation to investigate long-term safety after the end of Increlex® treatment and the possible occurrence of malignancies as well as other risks, the MAH has decided to expand the EU-IGFD registry into a global registry by involving additional countries where the product is registered and marketed, and to collect long-term safety data post-treatment for all participants regardless of duration of therapy.

Since this is a non-interventional observational registry, the decision to start treatment with Increlex®, and which tests and assessments to perform, will have been taken prior to the participant's inclusion in the study and therefore a limitation of the registry is that some key data may be missing. The assessments performed and data provided from different study sites may vary depending on each local site's routine clinical practice.

In particular, it is likely that some pre-treatment measures required to assess treatment effectiveness outcomes (height, height velocity, height SDS, weight, pubertal stage) may be missing and therefore the effectiveness assessments may not be possible for all participants.

The determination of the lowest effective dose has been included as a secondary objective of this registry. The design of the registry being non randomized and without fixed dose, we have no certainty to be able to determine the lowest effective dose.

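### Immunogenicity is tabulated on the Safety Population although the protocol lists no record of who had an antibody test, so untested participants enter the denominator as non-events

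*Protocol*

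**What the plan says.** Protocol section 11.1.5 lists the targeted adverse events for the treatment period. One of them is "immunogenicity (presence of antibodies if available". For the post-treatment period the list is "All targeted AEs mentioned in the treatment period except lipohypertrophy at injection sites", so immunogenicity remains on it.

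Section 9.3.1.1 gives the primary endpoint as "Incidence of SAEs (including AESI of neoplasia), targeted AEs, all AEs, deaths and withdrawals due to AEs during Increlex® treatment". Section 9.7.2.5 states: "The primary analyses and summary tables of safety data will be based on the Safety Population (data from the treatment period only"). The overall summary table of adverse events, with targeted events as one of its categories, "will be presented with the number and proportion of participants and the number of events". Incidence is then tabulated by system organ class and preferred term. Section 9.7.2.6 plans the same tables for the post-treatment period.

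Section 9.7.1 defines the Safety Population as "all participants who have taken the treatment at least once and with at least one follow-up visit", or with post-treatment safety data. Antibody testing plays no part in the definition.

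On collection, section 9.6.1 refers to Table 1 for the data gathered at each visit. Table 1 has a general row, "All AEs, SAEs, AESI, targeted AEs and special situations", and no antibody row. Sections 9.2.7.1 to 9.2.7.3 and 9.3.2.2 have no such item either. The only antibodies mentioned elsewhere are those against growth hormone, in eligibility and baseline aetiology. Section 9.4 requires no additional procedures beyond quality of life and post-treatment safety follow-up.

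**The concern.** Most targeted events can come to light at an ordinary visit through a complaint or an examination. Immunogenicity cannot: as defined, it exists only if a laboratory test was run. The preferred way of eliciting events in section 11.2.1, open questioning of the participant, will not reveal an antibody.

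A positive result creates an adverse event record. A negative result and an unperformed test both create nothing, and the listed data do not tell them apart. The rule in section 9.7.2.1 that missing data are displayed does not help, because a test that was never done leaves no empty field to display.

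Other targeted events that lean on a test are better served. Echocardiogram and funduscopy have their own row in Table 1 and their results are listed in section 9.3.2.2, which supports cardiomegaly and papilloedema. For hypoglycaemia, suspected events count as well, and glucose is recorded where available.

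At stake is a low immunogenicity percentage in successive interim reports of an open-ended registry that may reflect little testing and that a reader could not correct.

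**Working it through.** **What is there to reproduce.** The protocol states no immunogenicity rate, no fraction tested and no sample size, so there is no figure of its own to check. Every number below is assumed for illustration.

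**What the table would show.** Let N be the Safety Population, n the number tested, x the number positive, f = n/N and q = x/n.

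- Tabulated proportion = x/N = f × q. This is an identity.
- True proportion = f × q + (1 − f) × u, where u is the unknown positivity among the untested.
- Shortfall = (1 − f) × u.

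If the assay is accurate, the tabulated figure can equal the true one but not exceed it. They are equal only if no untested child would have tested positive. Neither f nor u can be obtained from the data the protocol lists.

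**Illustration 1: testing unrelated to antibody status.** Here q equals the true proportion. With an assumed true value of 50%:

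| f | tabulated |
|---|---|
| 5% | 2.5% |
| 10% | 5% |
| 20% | 10% |
| 50% | 25% |
| 100% | 50% |

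With a true value of 10% and the same values of f, the tabulated figure runs from 0.5% to 10%. With 80% it runs from 4% to 80%.

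**Illustration 2: precision.** Assume N = 100 and n = 20, with exact 95% intervals.

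| positives | on N = 100 | on n = 20 |
|---|---|---|
| 10 | 10.0% (4.9 to 17.6) | 50.0% (27.2 to 72.8) |
| 0 | upper limit 3.6% | upper limit 16.8% |

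The interval on the full denominator is too narrow, because it treats the 80 untested children as observed negatives. With 10 positives and 80 untested, the true proportion among the 100 could lie anywhere from 10/100 = 10% to (10 + 80)/100 = 90%.

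**Illustration 3: testing prompted by symptoms.** Assume 20 of 100 children are truly positive, 20 are tested, and the tested group contains 10 of the positives.

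- Tabulated: 10/100 = 10%.
- Positives over tested: 10/20 = 50%.
- True: 20%. Check: f × q = 0.20 × 0.50 = 0.10; u = 10/80 = 0.125; (1 − f) × u = 0.80 × 0.125 = 0.10; sum 0.20.

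The Safety Population figure is too low and the positives-over-tested figure too high. Neither should be shown without the number tested and the reason for testing.

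**The case against.** The case on the other side has several parts.

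- **The denominator is not fixed term by term.** Section 9.7.2.5 gives number and proportion for the overall summary by category. For individual terms it says only that incidence is tabulated. The SAP is not shown and could set a different denominator. This is fair, but the Safety Population is the stated basis for these tables. A SAP also could not restrict to tested participants without a variable that the protocol does not list.
- **The limitation is disclosed.** The definition itself is conditional, and section 9.9 says: "The assessments performed and data provided from different study sites may vary depending on each local site's routine clinical practice". That is a warning, but its specific examples are effectiveness measures and it says nothing about an adverse event denominator.
- **A non-interventional registry cannot require the test.** This stands. The absence of a mandated antibody test is a design constraint, not an error. The gap is that testing is not recorded when it happens.
- **Under-ascertainment affects all adverse events.** Sleep apnoea or hearing loss also need someone to look. That is true, but immunogenicity is the one defined purely by a laboratory result without a matching collection item. It is also only one of 18 targeted events, in a descriptive registry whose main concern is neoplasia, and this limits the weight of the point.

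A reader might also infer that the protocol classes untested children as antibody-negative. It does not; they are simply non-events in the table. Nor can it be said as fact that the eCRF lacks a testing field, since the form is not shown. Its absence is inferred from section 9.6.1 and Table 1.

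**Conclusion.** The point holds. As written, the tabulated immunogenicity incidence is the fraction tested times the positivity among those tested, with untested participants counted in the denominator as non-events. It understates the proportion who form antibodies by an amount that the listed data cannot determine.

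A reader might go further and quote a fold-range, for instance 2- to 10-fold if 10% to 50% are tested. The protocol does not support this. It gives no testing fraction, and the range holds only if testing is unrelated to antibody status, which is doubtful if hypersensitivity or poor growth response prompts the test. A reader might equally conclude that positives over tested should simply replace the Safety Population proportion; Illustration 3 shows how that figure can err upward.

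The conclusion rests on Table 1, the visit lists and the safety variables being the full account of what is collected, and on an accurate assay. It affects one component of a broad descriptive endpoint and is best treated as an inexpensive improvement.

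**What to change.** Add one item to Table 1 and to sections 9.2.7.2, 9.2.7.3 and 9.3.2.2 for any anti-IGF-1 antibody test done in routine care: done (Yes/No), date, assay, result and reason for testing. State that the registry requires no new test.

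In sections 9.7.2.5 and 9.7.2.6, state that immunogenicity is presented as number positive, number tested (with positives over tested and its confidence interval) and number not tested, alongside the Safety Population N. Add that the Safety Population proportion is not to be read as the incidence of antibody formation.

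The cost is a small data-entry burden and a short addition to the analysis text. The positives-over-tested figure will be less precise and may be biased upward where symptoms prompt testing. That is why the reason for testing and the number untested belong beside it.
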